## Risk & Benefit

**Risk** – Subjects may experience recurrence, lack of infection resolution, and/or adverse drug reaction.

**Benefit** – Subjects may be free from hospitalization sooner and have a reduced risk of catheter-related bloodstream infection.

## Statistical Analysis Plan

**Sample Size** – Prospective randomized institutional pilot trial of 20 subjects. This is a pilot post-operative institutional trial to ascertain safety and compliance therefore sample size is adequate. Appropriate statistical analyses will be conducted such as T-tests, ANOVA, correlations, linear and logistic regression.

**Data Safety Monitoring** – Specify whether there will be a safety data monitoring plan implemented for the project. This is an ongoing review of the study, actions, data collection, and analysis throughout the entirety of the project.

A Data Safety Monitoring Committee will be formed with clinicians within the Heart & Vascular Institute and Department of Medicine, Section of Infectious Disease as well as a biostatistician consult. Data will be reviewed at when N=1 subjects are enrolled into each arm, again when N=4 are enrolled into each arm, and then again at the end of the study.

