## **Objectives**

**Purpose** – *The purpose of this post-operative institutional pilot trial is to ascertain the safety and compliance of initial IV antibiotic followed by oral therapy following uncomplicated IVDA endocarditis. Endocarditis has a high rate of morbidity and mortality, involves prolonged hospitalization and prolonged use of IV antibiotics necessitating six (6) weeks of in-patient stay, and comes with a high cost.*

**Primary Objective** – *To assess all-cause mortality, recurrent blood culture positive infection, or cardiac re-operation at six (6) months and twelve (12) months.*

**Secondary Objective(s)** – *To assess all-cause mortality, readmission for recurrent infection or cardiac re-operation, and cost at six (6) and twelve (12) months.*

**Rationale:** *The key principle of this hybrid pathway (regional or smaller scale trial) is to focus on both “implementation science” and “effectiveness”:*

- **Effectiveness:** *This study will document that in postoperative patients who have undergone valve repair or replacement as treatment for IV drug–associated (IVDA) endocarditis:*

- Will ascertain safety and compliance for 2 weeks of postoperative IV antibiotics followed by 4 weeks of oral antibiotics versus 6 weeks of conventional postoperative IV antibiotics
- **Implementation science:** This study will document that patients managed with either arm of the protocol can achieve compliance with and graduation from a drug rehabilitation program. The implementation science portion of this trial will place particular emphasis on the measurement of compliance (e.g. a centrally managed core site mobile Medisafe compliance program [<https://www.medisafe.com/>]).

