#### **Exclusion:**

- Inability to give informed consent
- Residual infection requiring IV antibiotic therapy
- Any persistent secondary noncardiac infection (e.g. infections of solid organs or joints)
- Known poor compliance or deemed incapable to comply with the compliance tracking tool
- Reduced absorption or inability to receive oral treatment due to a gastrointestinal disorder
- Endocarditis attributed to fungal organisms.
- Cancer not otherwise in remission or in need of current or future oncologic therapy
- Medically immunocompromised state
- History of habitual noncompliance
- Pregnancy
- Mental incapacity
- Unable to perform local or institutional medical and psychiatric follow up
- Unstable home environment
- Inadequate access to mobile cell service (geographic/rurality)

**Study Design** – Prospective randomized institutional pilot trial of 20 subjects.

Both groups will receive the following support:

1. All patients will enroll in aggressive drug rehabilitation with mandatory participation in a formal psychiatric rehabilitation program for a minimum of 6 weeks (combined inpatient and outpatient),
2. All patients will be followed closely by specialists in Infectious Disease
3. All patients will undergo monitoring of treatment efficacy with serum antibiotic levels during the treatment phase
4. All patients will undergo surveillance monitoring of treatment efficacy with blood cultures, and
5. All patients will participate in a compliance tracking tool for medication administration (e.g. a centrally managed core site mobile Medisafe compliance program [<https://www.medisafe.com/>]. All patients and their family/primary care givers receive Medisafe compliance training).

**Patients:** Postoperative patients who have undergone valvar repair or replacement for IVDA endocarditis may be prospectively randomized into two arms:

1. Group I (Experimental Group): 2 weeks of postoperative inpatient IV antibiotic therapy followed by 4 weeks of oral therapy with outpatient follow-up.
2. Group II (Control Group): conventional 2 weeks of postoperative inpatient IV antibiotic therapy followed by 4 weeks of IV antibiotic therapy (inpatient or facility supervised if indwelling catheter utilized).

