Subjects will be identified by the study investigators and research coordinators. Once Inclusion and Exclusion criteria have been met, the patient will be approached by the primary surgeon and/or study investigator to present the study. If the patient indicates interest in the study, the study investigator will collaborate with the research coordinator to obtain informed consent.

**Study Duration** – Subjects will be followed for twelve (12) months. Enrollment is expected to take one (1) year to achieve our proposed sample size. Data collection will occur real-time throughout the study and data analysis will be performed at the conclusion of the study.

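### The plan calls 20 subjects adequate to ascertain safety without support; about 10 per arm with no events still allows true event rates up to roughly 26–31%

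*Combined protocol and SAP*

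**What the plan says.** The Sample Size paragraph of the Statistical Analysis Plan describes a "Prospective randomized institutional pilot trial of 20 subjects" and continues: "This is a pilot post-operative institutional trial to ascertain safety and compliance therefore sample size is adequate". Target Population & Recruitment Methods uses the same words. This is the whole justification.

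The Rationale in Objectives makes the claim comparative. Its Effectiveness bullet reads "Will ascertain safety and compliance for 2 weeks of postoperative IV antibiotics followed by 4 weeks of oral antibiotics versus 6 weeks of conventional postoperative", the comparator being the full intravenous course. The primary objective is "To assess all-cause mortality, recurrent blood culture positive infection, or cardiac re-operation at six (6) months and twelve (12) months".

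On analysis, the plan offers only "Appropriate statistical analyses will be conducted such as T-tests, ANOVA, correlations, linear and logistic regression". It gives no significance level, confidence level, margin, expected event rate, decision rule or allowance for loss over the twelve-month follow-up. Study Design & Methodology adds that future studies can build on the results.

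**The concern.** The sentence infers adequacy from the trial being a pilot and ties that adequacy to ascertaining safety. Being a pilot can explain why a trial is small. It does not show that a small trial answers a safety question.

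The safety outcome is a composite of death, recurrent culture-positive infection and cardiac re-operation. A plan that promises to ascertain safety against the full IV course, lists mainly tests and regressions, and mentions no interval estimates leaves room to present a few event-free patients, or a non-significant comparison, as evidence that oral step-down is safe. A larger trial could then start from that conclusion.

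**Working it through.** **The plan's own figure.** N=20 cannot be reproduced, because the documents give no input to a sample-size or precision calculation. What can be checked is how much 20 patients would show.

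**Inputs**
- Total of 20 (Statistical Analysis Plan) and two arms: patients "may be prospectively randomized into two arms" (Study Design).
- Allocation ratio: not stated. I assume 10 per arm. This fits the symmetric review triggers ("Data will be reviewed at when N=1 subjects are enrolled into each arm, again when N=4 are enrolled into each arm"). I also show 8 to 12 per arm.
- Event rates, a 95% confidence level and Fisher's test at two-sided 0.05: my assumptions.

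**1. One arm, zero events.** The exact (Clopper-Pearson) upper limit for 0/n is 1 − 0.025^(1/n) two-sided and 1 − 0.05^(1/n) one-sided.

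| n in arm | two-sided 95% | one-sided 95% |
|---|---|---|
| 8 | 36.9% | 31.2% |
| 9 | 33.6% | 28.3% |
| 10 | 30.8% | 25.9% |
| 11 | 28.5% | 23.8% |
| 12 | 26.5% | 22.1% |

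At n=10, 1/10 events gives a two-sided interval of 0.3% to 44.5%, and 2/10 gives 2.5% to 55.6%. A true 20% rate would still produce no events in 10 patients with probability 0.8^10 = 10.7%. Pooling both arms, which would not address the comparison, gives an upper limit of 16.8% for 0/20.

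**2. Difference between arms.** With 0/10 v 0/10, the Miettinen-Nurminen score limit solves d²/[d(1−d)/10 × 20/19] = 1.96². This gives d = 3.84/(3.84 + 9.5) = 0.288, so the interval is about ±29 points. With 1/10 v 1/10, numerical inversion gives about ±34 points.

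**3. Test.** The Fisher p-value is 0.087 for 0 v 4 events and 0.033 for 0 v 5. With no control events, half the oral arm must therefore fail before p<0.05. With one control event, 6/10 gives 0.057 and 7/10 gives 0.020. Exact power by full enumeration at 10 per arm:

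| assumed true rates | power |
|---|---|
| 10% v 30% | 5.7% |
| 10% v 50% | 29.5% |
| 10% v 70% | 66.7% |

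A tripling from 10% to 30% would be missed about 94% of the time (100 − 5.7).

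**4. Scale.** By the normal approximation, 80% power for 10% v 30% needs [1.96√(2×0.2×0.8) + 0.842√(0.09+0.21)]²/0.2² = 61.6, so 62 per arm. Non-inferiority with a 10-point margin at a 10% rate (one-sided 0.025, 80% power) needs (1.96+0.842)² × 2 × 0.1 × 0.9/0.1² = 141.3, so 142 per arm. These figures show scale only; they are not a proposed size.

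**5. Compliance.** The adequacy sentence also covers compliance. By symmetry with 2/10 above, 8 of 10 compliant gives 100 − 55.6 = 44.4% to 100 − 2.5 = 97.5%. That is wide, but it may be acceptable for describing feasibility if it is stated in advance. The plan sets no precision goal here either.

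**The case against.** The best defence is that this is openly a pilot. The protocol calls it one repeatedly, describes it as regional or smaller in scale, and looks ahead to further studies. Its primary objective is to assess the composite, which can be read as descriptive. Measuring compliance is a normal pilot aim. All of this stands, and it is why the sample size itself need not change. It does not repair a sentence that ties adequacy to ascertaining safety, and no other section withdraws that claim.

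Three stronger readings go beyond the documents:
- A reader might call the adequacy claim false. The plan states no margin, power or precision that could be falsified, so the claim is unsupported.
- A reader might infer that a null result would be reported as safety. The plan defines no test of the composite, no success rule and no non-inferiority claim. Its wording permits the misreading but does not prescribe it.
- A reader might take the Effectiveness bullet to promise proof of effectiveness. That word is only a label; the garbled text beneath it speaks of safety and compliance.

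It is also fair to say that the power figures are secondary, since they rest on rates and a test that the plan does not give. The zero-event limits need only the arm size and a confidence level.

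**Conclusion.** The concern holds as a matter of unsupported adequacy. The plan says 20 subjects suffice to ascertain safety, gives no basis, and has a design that cannot do it at any useful precision. The best possible observation in the oral arm, no events, leaves true rates of about a quarter to a third open. An event-free comparison leaves differences of nearly 30 points open in either direction.

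The exact figures depend on the unstated 1:1 split and on 95% limits. The conclusion does not: from 8 to 12 per arm the two-sided limit never falls below 26%. Loss to follow-up would widen the intervals further. Misreading a null result as safety is a real risk that the wording leaves open; it is not a stated rule.

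**What to change.** Keep N=20 and make three wording changes.

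1. In Sample Size and in Target Population & Recruitment Methods, replace the adequacy sentence with text such as: *N=20 is chosen for feasibility and to describe compliance. Assuming 10 patients per arm, zero events in an arm is compatible with a true rate up to 31% (two-sided exact 95% limit), and with no events in either arm the 95% interval for the risk difference is about ±29 points, widening as events occur.* Confirm the allocation ratio and update the figures if it is not 1:1.
2. In the Statistical Analysis Plan, state that the primary composite will be reported by arm and as a risk difference, with exact or score 95% confidence intervals. Add that neither an absence of events nor a non-significant difference will be taken as evidence of safety, equivalence or non-inferiority.
3. In Objectives, reword the Effectiveness bullet so that the study will estimate safety outcomes and compliance in each arm with 95% confidence intervals. Reword the implementation-science sentence separately, as estimating the proportions who comply with and graduate from the rehabilitation program. One substitution will not read properly in both places.

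The changes need no extra patients, visits or data. The cost is that the stated claim becomes less favourable.

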## Safety Monitoring & Unanticipated Event Reporting

The study investigators along with the research coordinator will monitor data collected on subjects. If there are any events of concern, the research coordinator will work with the study investigators to assess the event and determine the next steps for adjudication and reporting, if applicable.

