## Study Duration & Timeline

Subjects will be followed for twelve (12) months. Enrollment is expected to last one (1) year. Data collection will occur real-time throughout the study and data analysis will be performed at the conclusion of the study.

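### The first two safety committee reviews are tied to enrolment rather than completed treatment, and none is then scheduled until study end, about 19 months later at the planned accrual

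*Combined protocol and SAP*

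**What the plan says.** Under Data Safety Monitoring, the Statistical Analysis Plan forms a committee and gives it three reviews. The first two are set by enrolment: "Data will be reviewed at when N=1 subjects are enrolled into each arm, again when N=4 are enrolled into each arm". The third comes "and then again at the end of the study". The section names no criteria for action and no unscheduled meeting.

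The design is described as "Prospective randomized institutional pilot trial of 20 subjects", with patients who "may be prospectively randomized into two arms". Neither the allocation ratio nor the randomisation method is given. On timing, Study Duration & Timeline states: "Subjects will be followed for twelve (12) months. Enrollment is expected to last one (1) year". The primary objective is "To assess all-cause mortality, recurrent blood culture positive infection, or cardiac re-operation at six (6) months and twelve (12) months". The arms differ only in the 4 weeks after the initial 2 weeks of IV treatment.

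For the time between committee reviews, Safety Monitoring & Unanticipated Event Reporting says: "The study investigators along with the research coordinator will monitor data collected on subjects". The same people assess events of concern and settle the next steps. Referral to the committee is not mentioned.

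**The concern.** A count of enrolled patients does not measure how much safety information exists. On the day a trigger is met, the newest patient has no follow-up at all. Reviews set this way can come before the treatment difference has had time to show itself.

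The second issue is the gap. After the 4-per-arm review, the next scheduled review is when the study is over and every later patient has been enrolled, treated and followed. The trial's stated purpose is safety and compliance, and its Risk section names recurrence and failure to clear infection. An excess of such events on oral therapy would matter most while patients are still being enrolled and treated, and in that period the committee has no scheduled look.

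**Working it through.** **Inputs.** From the documents: 20 patients, two arms, 1 year of enrolment, 12 months of follow-up each, a 4-week phase in which the arms differ, and a primary outcome at 6 and 12 months. Assumed: even accrual (one patient every 12/20 = 0.6 months, the first at month 0.6), time counted from enrolment at the start of the 4-week phase, and 1:1 allocation balanced at the 2nd and 8th patients. Four weeks is taken as 0.92 months.

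**Review 1 (1 per arm, 2 enrolled).** Month 2 × 0.6 = 1.2. Follow-up is 0.6 and 0 months, so 0 of 2 have finished the 4 weeks.

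**Review 2 (4 per arm, 8 enrolled).** Month 8 × 0.6 = 4.8. Follow-up is 4.2, 3.6, 3.0, 2.4, 1.8, 1.2, 0.6 and 0 months.
- Past the 4-week phase: 6 of 8.
- At 6 months: 0 of 8.
- Person-months: 0.6 × (0 + 1 + … + 7) = 16.8, against 20 × 12 = 240 planned, or 7%.

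**Review 3 (study end).** The last patient enters at month 12 and finishes at month 24. The gap is 24 − 4.8 = 19.2 months.

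**Patients entering after review 2.** With balance at patient 8, 20 − 8 = 12 (60%). This is the maximum, because imbalance delays the trigger. Under simple randomisation the chance of exactly 4 and 4 at patient 8 is 70/256 = 27%. By simulation (200,000 runs) the trigger then falls at 10.2 enrolled on average, leaving about 10. With a fixed 10/10 split in random order the median is 9 enrolled, leaving 11.

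**Slower accrual.** If enrolment took 18 or 24 months, 1 or 3 of the 8 would have reached 6 months at review 2.

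**What review 2 could show.** The documents give no event rate, so the rates here are assumptions. Let p be the 6-month failure risk on oral therapy, with constant hazard λ = −ln(1 − p)/6. The chance of no failure among the 4 oral patients is exp(−λ × total oral follow-up). With alternating allocation, that follow-up is 4.2 + 3.0 + 1.8 + 0.6 = 9.6 months or 3.6 + 2.4 + 1.2 + 0 = 7.2 months, giving (1 − p)^1.6 or (1 − p)^1.2. With full 6-month follow-up it is (1 − p)^4.

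| Assumed p | No failure seen at review 2 | No failure seen with full 6 months |
|---|---|---|
| 10% | 84–88% | 66% |
| 30% | 57–65% | 24% |
| 40% | 44–54% | 13% |

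The hazard shape matters. If the same 30% all fell evenly in the first 3 months, the range would be 0.7^2.8 to 0.7^2.2, or 37–46%.

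**Timing of the alternative triggers, without pausing enrolment.**
- 1 per arm past the 4 weeks: 1.2 + 0.92 = month 2.1, 3 enrolled.
- 4 per arm past the 4 weeks: 4.8 + 0.92 = month 5.7, 9 enrolled.
- 7 per arm past the 4 weeks: 8.4 + 0.92 = month 9.3, 15 enrolled.
- 4 per arm at 6 months: 4.8 + 6 = month 10.8, 18 enrolled.

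**The case against.** The strongest reply is that review 2 has real content. About 6 of 8 patients will have finished the 4-week phase, and death, a positive culture or a re-operation is visible when it happens, not only at month 6. Surveillance cultures and real-time data collection are planned. This stands: review 2 lacks 6-month outcomes but does not lack safety data.

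Allocation also matters. Under simple randomisation the trigger tends to come later, with more follow-up. At least one patient has reached 6 months in about 34% of trials (trigger at the 11th patient or later: 352/1024). At an assumed 30% risk, the average chance of seeing no oral failure falls to about 48%. This also stands, and it is why 12 is an upper limit. Small numbers are part of the problem too: even with full follow-up, 4 patients would show no failure 24% of the time at a 30% risk.

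The alternative triggers have limits of their own. By the 6-month trigger, 18 of 20 patients are already enrolled.

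Two stronger readings are tempting. A reader might infer that the committee is unable to act between reviews. The documents do not say so: nothing bars an unscheduled meeting, and the investigators do assess events of concern. What is missing is a scheduled opportunity and a stated route. A reader might also infer that the committee is the trial's only independent protection. The plan never calls it independent, and its clinicians come from within the institute and the infectious disease section.

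In the other direction, the Statistical Analysis Plan has a sentence describing monitoring as continuing throughout the project. It follows an instruction to the author to specify whether a monitoring plan exists, so it reads as leftover template text. It schedules no further committee review.

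**Conclusion.** The point holds as a weakness in the timing of committee review and should be fixed. At the planned pace with balanced allocation, review 1 has no patient past the 4-week phase. Review 2 has about 6 of 8 past it, none at 6 months and 7% of planned person-months. The following 19 months, covering the entry and treatment of up to 12 of 20 patients (about 10 on average under simple randomisation), contain no scheduled committee review and no stated referral route.

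The enrolment trigger and the absence of a scheduled review before study end come directly from the text. The months and counts rest on even 12-month accrual and balanced 1:1 allocation. The detection figures rest further on assumed failure rates and a constant hazard, and should be quoted only as a range. The schedule contradicts no other part of the plan and invalidates no analysis. Randomisation without stated blocking is a separate matter.

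**What to change.** In Data Safety Monitoring, replace the enrolment triggers and fill the gap:

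1. Hold the first two reviews when 1 and then 4 patients per arm have completed the 4-week randomised phase.
2. Add a review when about 7 per arm have completed that phase, and one when 4 per arm have reached 6 months. These fall only about 1.5 months apart (10.8 − 9.3) and may be combined.
3. Keep the end-of-study review.
4. At each review, tabulate primary-composite events to date by arm, with follow-up time.
5. In Safety Monitoring & Unanticipated Event Reporting, state that primary-composite events arising between reviews are forwarded to the committee.

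The cost is wording and about one or two extra short meetings of a committee already being formed. No patients are added, and enrolment need not pause. The gain from moving review 2 alone is modest: at an assumed 30% risk, 0.92 more months for each of the 4 oral patients changes the chance of seeing no failure from 57–65% to 0.7^(13.28/6) to 0.7^(10.88/6), or 45–52%. The later reviews come when most patients are enrolled, so they mainly protect those still in treatment or follow-up.

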## Safety Monitoring & Unanticipated Event Reporting

The study investigators along with the research coordinator will monitor data collected on subjects. If there are any events of concern, the research coordinator will work with the study investigators to assess the event and determine the next steps for adjudication and reporting, if applicable.

